After receiving interest of a potential participant and consent form has been received researchers would then reach out via phone call to provide a more comprehensive description of the project, screening, and informed consent. Participants will be fully informed that they are free to stop their participation at any time. Candidates will need to pass a brief quiz testing their understanding that participation is completely voluntary. Participants will be required to answer questions demonstrating that they understand what type of data will and will not be collected from them over the upcoming months (self-report and FOCUS use data). Each question will need to be answered correctly before individuals can proceed to provide consent. Individuals who commence the study will be assigned to their sites practice facilitator (external or internal). Randomization will occur at the site level with equal representation of urban and rural settings in each implementation arm.

Staff Participants who will participate in on-site data collection evaluating implementation outcomes and clinic characteristics will be purposively selected from CMHC (both study arms) and from CMHC

administration/budget/finance offices (for costing). The assessment evaluating implementation outcomes will be fully explained to staff participants via webpage (hosted by Qualtrics), where staff can check a box to indicate they are willing to participate. Assessments time points will be at 0M (prior to their patient beginning treatment), then at roughly 3M (time-point after the patient completes treatment). The confidential survey takes 20-30 minutes to complete (questions are included in the supportive documents) and staff will be compensated \$20 in the form of an Amazon gift card for their time. Staff key informants will complete interviews with a trained member of the research team related to costing, including questions about services and effort put towards the study. Key informant interviews will last approximately 60 minutes and be audio-recorded, and later transcribed. Numbers will be provided at aggregate levels, or if treatments were specified, would not identify the individual.

4.2 Recruitment materials.

a. What materials (if any) will you use to recruit and screen subjects?

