The FOCUS application uninstalls at 3 months and then the 3 month web-based outcome assessment will be sent via text and will ask participants to complete it in a private and quiet space. Once again those who express difficulty completing the assessment through the web-based platform can request a call with an assessor on the research team. Participants who complete treatment will be mailed out a certificate of completion to their home address or clinic (based on participant's choice). They will no longer have access to the app, nor will participate in weekly calls for the next 3 months. They would then be sent another assessment at 6 months to complete.

Patient Participant Assessment:

Patient participants will receive a text from researchers just before their assessment date providing instructions on how to complete the online assessment. They will then be invited to conduct assessments at 0, 3, and 6 months via embedded link to a secure study portal (Qualtrics). For participants who need additional assistance, they can come into the participating clinic to complete on a tablet provided by the research team. Patient participants will receive \$30 compensation for each completed assessment (estimated completion time < 45 minutes) for a maximum of \$90 compensation (Plus additional \$10 each assessment to compensate data transmission or travel to site if more assistance is necessary). All participants will be paid for each assessment, but they will not be compensated for engagement in the intervention; assessments are administered to everyone enrolled in the study regardless of how/whether they engaged in FOCUS (note: all patient participants own working smartphones as part of inclusion criteria).

Assessments include questions about psychiatric treatment and hospitalizations, along with other measures of mental health including depression, anxiety, hearing voices, and recovery:

- Demographics and other characteristics
- PhQ9
- GAD-7
- Hospitalization- days hospitalized, no identifiers will be captured.
- ISI: Insomnia Severity Index
- Green Paranoid Thoughts Scale
- Symptom Checklist SCL-9Hamilton Program for Schizophrenia Voices Questionnaire (HPSVQ)
- Recovery Assessment Scale (RAS)
- Illness Management Recovery Scale (IMRS)
- Working Alliance Inventory (3M only)
- mHealth Mastery Measure (3M only)
- AIM
- Satisfaction

Information we plan to collect from EMR data:

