- A list of active participants will be generated either through culling EMR data or talking with clinical teams that will serve as the primary list for their clinical teams to approach to describe the study and gauge interest.
- Services billed- no identifiers will be shared with the research team

Mental Health Provider Participants:

Select mental health providers will be invited to complete an online assessment with the research team. Staff participants will be invited to complete a confidential online survey. This includes exposure to the FOCUS app, if strategies or the program was incorporated into their treatment plans, and perceptions of how the program was adopted and implemented at their clinic.

Mental Health Provider Assessment:

Providers who receive FOCUS data

- Offered mHealth, i.e., the percent of each practitioner's eligible patients who are offered FOCUS
- Treatment Initiation, i.e., percent of consenting patients who followed their practitioner's guidance and went on to download FOCUS onto their smartphone and interact with the system at least once. Dashboard Use, i.e., the average number of times each practitioner logs on to the online FOCUS dashboard to view their individual patients' uploaded FOCUS data

The following will be captured via online confidential** survey (Qualtrics):

- The perception among practitioners that an innovation is agreeable, palatable, or satisfactory. (Measured via AIM / IAM / FIM).
- ORIC: Organizational Readiness for Implementing Change

Providers at the clinic who may not have been directly involved with the FOCUS Intervention (to provide contextual factors) through online confidential survey (Qualtrics):

- Organizational Readiness to Change Assessment (ORCA)
 - CMHC staff participants will complete 23 items using a 5-point bipolar rating scale (1-Strongly agree to 5-Strongly disagree). Constructs evaluated include clinical cooperation within the practice, clarity in patient care goals and process, level of support (e.g., training, budget, staffing) and typical receptivity to guidance (staff) and feedback (leadership).
- Absorptive capacity will be measured among CMHC practitioners who were engaged in IF or EF implementation at 0, 3, and 6 months using the 14-item ACAP Scale.
 - o The ACAP Scale evaluates dimensions of absorptive capacity including
 - Acquiring (e.g., searching for new information, motivation to use information)

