Eligible staff from participating clinics will be asked to complete a confidential survey online prior to their patient starting treatment, then again after their participant completed the intervention (roughly 3 months later).

We would like to request a waiver for the stamp in order to make the form's contact information modifiable (highlighted text in both consent forms).

Costing Interview Key Informants:

Key informants will be selected from selected study sites to complete a costing interview via videoconferencing. Prior to initiating the audio-recorded interview, key informants will review the consent form and provide verbal consent which will be audio-recorded.

c. Comprehension. Describe how you will ensure or test the subjects' understanding of the information during the consent process.

Candidates will need to pass a brief quiz testing their understanding that participation is completely voluntary, how long the research study is and what confidentiality means. Participants will be required to answer questions demonstrating that they understand what type of data will and will not be collected from them.

	cause of the setting or thei	any subject groups that might find it difficult to say "no" to your r relationship with you, even if you don't pressure them to			
Examples: S into their he recruited fr	tudent participants being realthcare provider's resear	recruited into their teacher's research; patients being recruited ch, study team members who are participants; outpatients waiting room just prior to their surgery.			
X No Yes	→ If yes, describe what yo of the setting or relatio	ou will do, for each of these subject groups, to reduce any effect nship on their decision.			
	the researcher will not	dinator will obtain consent instead of the subjects' physician; know which subjects agreed to participate; subjects will have thearing about the study.			
	opportunities (if any) you	volves multiple or continued interaction with subjects over time, will give subjects to ask questions or to change their minds			
documentatio		ch of the statements below describe whether you will obtain uestion does not apply to screening and recruiting procedures uestion 4.6.			
documentation which have alrocumentation obtained by a	n of consent? NOTE: This que ady been addressed in que n of consent that is obtained method that allows verifications.	uestion does not apply to screening and recruiting procedures			

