## UNIVERSITY of WASHINGTON

Analytic Approach. Our analyses seek to test the overall effect of our implementation strategies on implementation outcomes (Aim 1), mediators and moderators of those effects (Aim 2), and the impact of the strategies on patient outcomes (Aim 3). In Aim 1, the dependent variables of interest will be penetration and provider acceptability assessed at baseline (prior to initiation of the facilitation strategies), at 3 months (following the completion of the facilitation period), and at 6 months (following 3 months of having no exposure to facilitation). Given the nested data (i.e., time nested within clinicians and clinicians nested within agencies), analyses will rely on 3-level mixed effects regression models. Negative binomial regression with log offsets will be used to model rates, and linear regression will be used to model continuous outcomes. For all models, our independent variables of interest will be a binary indicator of internal versus external facilitation (measured at the organizational level), time, and their interaction. The magnitude and statistical significance of the interaction term will estimate the effect of the implementation strategy on change, or "growth," in outcomes over time. The impact of the intervention strategy on each outcome at each time will also be derived from these models. In addition, we will aggregate facilitylevel data and estimate the average weighted cost metrics across the sample of sites. Future commercial pricing of mHealth technology is unknown, so we will run scenarios that have different ranges of costs for FOCUS and explore the impact on the total program costs.

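### The protocol ties the staff follow-up survey to patient completion and gives only two waves, whereas the SAP analyses provider acceptability at baseline, 3 and 6 months

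*Protocol*

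**What the plan says.** The protocol describes the staff survey schedule in two places. Both give a baseline before the provider's patient begins treatment and one follow-up:

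- Section 8.2b (Staff Participants): "then again after their participant completed the intervention (roughly 3 months later".
- Section 4.1 (Staff Participants): "then at roughly 3M (time-point after the patient completes treatment".

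The SAP (Analytic Approach) states for Aim 1 that "the dependent variables of interest will be penetration and provider acceptability assessed at baseline", with later waves "at 3 months (following the completion of the facilitation period), and at 6 months (following 3 months of having no exposure to facilitation". That is three waves, with no condition on what any patient did.

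Three other statements bear on the point:

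- Section 5.1 takes acceptability from the online staff survey ("Measured via AIM / IAM / FIM"), so this survey supplies an Aim 1 outcome.
- Section 5.1 gives another practitioner measure a fixed schedule: "Absorptive capacity will be measured among CMHC practitioners who were engaged in IF or EF implementation at 0, 3, and 6 months".
- For patients, section 5.1 says that "assessments are administered to everyone enrolled in the study regardless of how/whether they engaged in FOCUS". Staff have no equivalent sentence.

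The SAP (Power Analysis) plans 20 clinics, 5 clinicians per clinic and 3 patients per provider.

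**The concern.** Some patients will not reach completion. Section 5.1 treats starting FOCUS as an outcome to be measured, reserves a certificate for those who complete, and section 10.6 provides for withdrawal, for example on hospitalization or incarceration. If staff follow-up waits for completion, a provider whose patient falls into one of these groups has no stated survey date.

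Under the two-wave schedule in sections 4.1 and 8.2b, that survey is also the only post-baseline acceptability measure. A provider who misses it contributes a baseline value and nothing on change, and change by strategy is what the Aim 1 interaction term estimates.

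Patient completion happens after randomization, and either facilitation strategy could affect it. The SAP's Aim 1 models contain strategy, time and their interaction, and the SAP relies on likelihood-based ignorable analysis without modelling drop-out. That protects the comparison only if missingness is explained by what is in the model. If follow-up depends on completion, and completion is related to how acceptable the provider finds FOCUS, the model as described does not account for it.

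**Working it through.** **Step 1. The passages side by side**

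| Source | Waves for provider acceptability | What sets the post-baseline date |
|---|---|---|
| Protocol 4.1 | 0 and roughly 3 months | the patient completing treatment |
| Protocol 8.2b | before the patient starts, and roughly 3 months later | the patient completing the intervention |
| SAP, Aim 1 | baseline, 3 and 6 months | end of the facilitation period, then 3 months without facilitation |

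The sources differ in the number of waves and in the event that dates them. The protocol wording is also silent on two cases: a patient who does not complete, and a provider with more than one patient.

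**Step 2. How many providers could lack a trigger**

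The plan gives no figure to reproduce, so this is a sensitivity calculation.

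Inputs:

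- 3 patients per provider and 100 providers (SAP, Power Analysis).
- Probability q that a patient does not complete. 3.5% is the FOCUS dropout in the pilot EF trial (Protocol 1.8b, part C). The values 10%, 20% and 30% are assumptions. For context, the same trial reports 90% commencement, so about 10% did not start.
- Independence of patients within a provider (assumed). Clustering would raise the share under the first rule below and lower it under the third.

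Share of providers without a trigger under three possible rules, none of which the documents state:

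- any completer triggers the survey: q³
- one index patient triggers it: q
- all three patients must complete: 1 − (1 − q)³

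At q = 0.10 these are 0.1³ = 0.001, then 0.10, then 1 − 0.9³ = 1 − 0.729 = 0.271.

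| q | Any completer | Index patient | All three |
|---|---|---|---|
| 3.5% | 0.0% | 3.5% | 10.1% |
| 10% | 0.1% | 10% | 27.1% |
| 20% | 0.8% | 20% | 48.8% |
| 30% | 2.7% | 30% | 65.7% |

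With 100 planned providers, each percentage is also a count. At a given q, the unstated rule decides whether the loss is negligible or serious.

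**Step 3. What is and is not affected**

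Acceptability comes from the staff survey and is exposed. Penetration is not: section 5.1 defines it from offers, treatment initiation and dashboard use. No sample size or power figure in the SAP changes as a result of this point.

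**The case against.** The best reply is that completion is only a description of the calendar end of treatment. Both protocol passages give a time of roughly 3 months, and section 5.1 says the app uninstalls at 3 months. Section 8.2b is a lay consent description for the IRB rather than an operating procedure. The SAP, which governs the Aim 1 analysis, already sets fixed waves, and section 5.1 does the same for absorptive capacity. On that reading every provider is surveyed.

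Much of this stands. The calendar reading is available, and a reader who infers that providers of non-completers are excluded, or that acceptability is in fact selected on completion, goes further than the documents: no passage says so. Nor do they support inferring that the arm losing more patients would lose more of its dissatisfied providers and so hide an EF–IF difference. They report no link between completion and provider ratings, and no completion rates by arm.

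The size may also be small. Adding the pilot's 3.5% dropout to its roughly 10% non-commencement gives q = 0.135, a rough figure that may double count. If any completer suffices, 0.135³ is about 0.25% of providers.

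Missingness driven by completion would not be beyond repair either. FOCUS use is recorded by the system (section 5.2), so completion could be entered in the model, but the SAP does not say that it will be.

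The reply does not remove the conflict. The protocol directs when surveys go out, and the SAP can analyse only what is collected. The protocol also uses completion as a status that some patients will not reach, and the calendar reading does not supply the missing 6-month wave.

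**Conclusion.** The point holds as a conflict between protocol and SAP and as an undefined survey trigger. Read literally, sections 4.1 and 8.2b leave no defined follow-up for providers of patients who never start, stop or are withdrawn, and no rule for providers with several patients. They also omit the 6-month acceptability wave that the SAP analyses. Post-baseline acceptability may then depend on a post-randomization patient outcome that is absent from the Aim 1 models.

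At an assumed 10% independent non-completion with 3 patients per provider, the share without a trigger is 0.1%, 10% or 27%, depending on a rule the documents do not give. The direction and size of any bias between arms cannot be determined from them. The change should be made because it is cheap and because a survey that was never sent cannot be recovered at analysis.

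**What to change.** 1. In Protocol sections 4.1 and 8.2b, replace the patient-completion wording with fixed times that match the SAP: the end of the clinic's 3-month facilitation period, and 6 months. State the date from which these times are counted.
2. State that the survey goes to every provider with a baseline survey, whether or not any of their patients started, stopped or completed FOCUS, in parallel with the existing patient rule.
3. Reconcile the 6-month staff wave: add it to sections 4.1 and 8.2b, or amend the SAP if it is not intended.

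The cost is protocol wording, an IRB modification and $20 per additional survey. A 6-month wave for all 100 planned providers would be at most 100 × $20 = $2,000.

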9 PRIVACY AND CONFIDENTIALITY

9.1) Privacy protections. Is this research likely to leave subjects with a concern that their privacy is being/has been invaded?

Privacy refers to the sense of being in control of access that others have to ourselves. This can be an issue with respect to recruiting, consenting, sensitivity of the data being collected, and the method of data collection.

Examples:

- Many subjects will feel a violation of privacy if they receive a letter asking them to participate in a study because they have ____ medical condition, when their name, contact information, and medical condition were drawn from medical records without their consent. Example: the IRB expects that "cold call" recruitment letters will inform the subject about how their information was obtained.
- Recruiting subjects immediately prior to a sensitive or invasive procedures (e.g., in an outpatient surgery waiting room) will feel like an invasion of privacy to some individuals.
- Asking subjects about sensitive topics (e.g. details about sexual behavior) may feel like an invasion of privacy to some individuals.

No Ye → If y

→ If yes, describe the steps you will take, if any, to protect the privacy of subjects and potential subjects.

Participants may feel uncomfortable answering questions about their symptoms during assessments. Participants will be reminded that they are able to skip questions, take a break at any time, or let research staff know they no longer want to participate in the study. We can connect patient participants to their clinical staff if needed.

9.2 Identification of individuals in publications and presentations . Do you plan to use potentially identifiable information about subjects in publications and presentations, or is it possible that individual identities could be inferred from what you plan to publish or present?
No Ye → If yes, will you obtain subject consent for this use?
Yes No → If no, describe the steps you will take to protect subjects (or small groups of subjects) from being identifiable.
subjects) from being identifiable.
9.3 State mandatory reporting. Each state has reporting laws that require some types of individuals to report some kinds of abuse, and medical conditions that are under public health surveillance. These include:
 Child abuse Abuse, abandonment, neglect, or financial exploitation of a vulnerable adult Sexual assault Serious physical assault
 Serious physical assault Medical conditions subject to mandatory reporting (notification) for public health surveillance
Are you or a member of your research team likely to learn of any of the above events or circumstances while conducting your research AND feel obligated to report it to state authorities? No Ye If yes, the UW IRB expects you to inform subjects of this possibility in the consent form or during the consent process, unless you provide a rationale for not doing so:
(9.4) Retention of identifiers. Check the box below to indicate your assurance that you will not destroy any identifiers (or links between identifiers and data/specimens) that are part of your research records until after the end of the applicable records retention requirements (e.g. Washington State; funding agency o sponsor; Food and Drug Administration) for your research. See the "Research Data" sections of the following website for UW Records management for the Washington State research rectords retention schedules that apply in general to the UW (not involving UW Medicine data): http://f2.washington.edu/fm/recmgt/retentionschedules/gs/general/uwgsResearch#R
See the "Research Data and Records" information in Section 8 of this document for the retention schedules for UW Medicine Records: http://www.uwmedicine.org/about/Documents/UWMRRS-1.5.pdf X Confirm
9.5 Certificates of Confidentiality. Do you have or, are you planning to obtain, a federal Certificate of Confidentiality for your research data?
x No

I			Υe
ı		ı	S

9.6 Data and specimen security protections. Identify your data classifications and the security protections you will provide, referring to the **ZIPLINE GUIDANCE**: **Data and Security Protections** for the minimum requirements for each data classification level.

"Risk of harm" refers to the risk of harm that would occur with a breach of the unprotected or breached data.

Level	Data Classification
	Very low risk of harm if disclosed
	These data have very little or no sensitivity. Disclosure of these data would have very little
	or no risk of physical, psychological, social, economic, legal, or educational advancement
1	harm to the subjects.
1	
	Examples: De-identified, anonymous, or publicly available data, data for which subjects
	have consented to allow public access (e.g., a museum archive), opinions of individuals
	about non-sensitive issues or performance on non- sensitive tasks.
	Some risk of minor harm to individuals if disclosed
	These data have relatively little sensitivity except possibly short-term embarrassment or
2	psychological discomfort if the data were disclosed.
_	
	Examples: Performance of individuals on non-sensitive tasks in a competitive situation,
	genetic information about individuals' metabolism of medical drugs such as statins.
	Could cause risk of material harm to individuals if disclosed
	These data could result in harm that can have genuine impact, but the magnitude and/or
3	duration are generally not serious, long-lasting, and/or irreversible.
	Examples: Non-sensitive Personal Health Information.
	Would likely cause serious harm to individuals if disclosed
	These data could result in serious harm, if disclosed.
4	
	Examples: Sensitive Personal Health Information, such as the history of cancer or other
	significant conditions which could (for example) affect employability or insurability.
	Extremely sensitive; could cause severe harm to individuals if disclosed
	These data could result in serious and long-lasting harm, if disclosed.
5	
	Examples: Information about subjects' illegal behavior, very sensitive Personal Health
	Information such as the diagnosis of HIV/AIDS in some cultures, or a diagnosis of leprosy.

a. Which level of protections will you apply to your data and specimens? If you will use more than one level, describe which level will apply to which data and which specimens.

3

b. Use this space to provide additional information, details, or to describe protections that do not fit into one of the levels.

